## 7 Sample Size Justification

The study was originally planned to enroll up to 60 subjects. No formal hypothesis was being tested and therefore the sample size determination was not based on a statistical power calculation, but rather was considered sufficient to inform a baseline assessment on early post-operative outcomes.

## 8 Statistical Analysis Methods

### 8.1 General Conventions

Subject data will be summarized in tables and presented in further detail in listings. All eCRF data will be listed per subject for all subjects. Descriptive statistical analyses will be provided for pre-specified study endpoints. Summaries for continuous variables will include a minimum of number of observations (n), mean, standard deviation, median, minimum, and maximum. Summaries for categorical variables will include number and percentage.

Analyses will be conducted using SAS software. During the course of programming of tables for summaries that are described in this SAP, minor modifications may become necessary. Examples of these minor modifications include, but are not limited to, re-wording of a footnote, addition of a footnote, re-labeling of a column, or addition or removal of a column from a listing. In cases where modifications to tables or listings are not related to a change in statistical analysis methodology or conclusions that could be made on the originally proposed

methodology, then no amendment of the SAP is necessary. Changes to planned analyses specified in the protocol or alterations of an approach that is described herein, will require an amendment to the SAP.

Baseline for all parameters will be defined as the last available measurement on or before the procedure date.

## 8.2 Disposition of Study Subjects

Subject disposition will be summarized in total using counts and percentages. The number and percentage of subjects in the FAS who completed and discontinued will be tabulated along with the specific reasons for discontinuation.

## 8.3 Demographic and Baseline Characteristics

Summary statistics of subject demographics (age, sex, race, and ethnicity) will be presented for the FAS. Vital signs (height, weight, body mass index, systolic blood pressure, diastolic blood pressure, heart rate and ASA score) will be summarized in a similar manner.

Counts and percentages will be provided for medical history terms presented by Medical Dictionary for Regulatory Activities (MedDRA) System Organ Class and Preferred Term. Data collected in the Urologic or Other Relevant Procedure History eCRF will be listed.

Summary statistics will be provided for quantitative parameters collected in the Complete Blood Count (CBC) and Complete Metabolic Panel (CMP) blood draws reported at the Screening/Baseline Visit. Urinalysis and culture test results will be listed.

## 8.4 Clinical Characteristics

Pre-operative clinical characteristics as well as procedure day measurements will be summarized at both the subject level as well as the kidney stone level given that many subjects present with more than one stone for treatment in the study. At the subject level, counts and percentages will be provided for whether the left or right kidney is being treated, as well as the number of stones per subject. Summary statistics will be provided for cumulative stone burden, defined as the sum of the longest dimension of all stones, estimated percutaneous tract length, and cumulative stone volume which is calculated for each stone as  $(\pi/6) * x \text{ dimension} * y \text{ dimension} * z \text{ dimension}$ , then summed across all stones.

At the stone level, counts and percentages will be provided for the pole location and sub-location and summary statistics will be provided for the longest linear dimension and stone radio density.

## 8.5 Primary Endpoint and Associated Hypotheses

No formal hypotheses are specified for this study.

The primary endpoint is the successful completion of the robotic-assisted kidney stone removal procedure, defined as using robotic-assistance provided by the MONARCH™ Platform, Urology to achieve the following procedure milestones:

- Gain safe concomitant (i.e., retrograde and antegrade) access to the upper urinary tract
- Locate and visualize the kidney stones
- Enable fragmentation of stones by standard of care method
- Evacuate stone fragments and dust
- Complete treatment without need for case conversion, as assessed by the investigator

As indicated in the study protocol, the above bulleted device endpoints will be assessed regardless of clinical outcome (e.g., evacuation of stone fragments and dust may still be achieved by the device even if the patient is not stone free). Additionally, these milestones are considered successfully achieved if done so using robotic assistance provided by the MONARCH™ Platform, Urology at any point during the procedure (e.g., location and visualization of kidney stones may still be achieved with robotic assistance, even if the Investigator occasionally chooses to drive the ureteroscope manually due to physician preference.) Alternatively, an early termination of the robotic procedure due to malfunction of the robot, and a subsequent conversion of the case to conventional procedure, would indicate that “complete treatment without need for case conversion, as assessed by the physician” had not been achieved.

The number and percentage of subjects experiencing successful completion will be summarized and an exact 95% confidence interval will be estimated. Counts and percentages will also be provided for each of the four components of the primary endpoint.

## 8.6 Secondary Endpoints and Associated Hypotheses

The following secondary endpoints are specified for this study:

- Stone free rate ( $\leq 4$  mm residual fragments, measured 30-days post-operative)
- Adverse events through 90-days post-operative, scored on the Clavien-Dindo scale
- Conversion to conventional treatment methods due to study device-related safety event

No associated hypotheses are specified.

The stone free rate will be computed as the percentage of patients who are stone free assessed by computed-tomography (CT) scan at post-operative Day 30. Stone free is defined as having  $\leq 4$  mm residual cumulative stone burden detected by CT. Patients who are found to not have any residual stone fragments at Day 1, will not undergo a second CT at post-operative Day 30, and will be presumed to be stone free at Day 30 for this calculation. The number and percentage of procedures resulting in a subject who is determined to be stone free at Day 30 will be

summarized and a 95% confidence interval will be estimated. Similar analyses will be performed for the stone-free rate at Day 1.

All adverse events will be captured up to post-operative Day 90, at which point the subject exits the study. Summaries will be provided for all adverse events by MedDRA System Organ Class and Preferred Term. Similar summaries will be provided for device-related AEs, procedure-related AEs, serious adverse events (SAEs), device-related SAEs, and procedure-related SAEs. Adverse events will also be scored on the Clavien-Dindo scale and summaries will be provided by System Organ Class and Preferred Term for events that are graded at III or higher on the Clavien-Dindo scale and then similarly for those that are Grade II or lower in a separate output table.

The number and percentage of procedures converted to conventional stone removal procedures (e.g., ureteroscopy or percutaneous nephrolithotomy) due to the occurrence of a study device-related safety event will be summarized. A qualifying safety event is a study device-related adverse event that occurs during the study procedure that prompts the physician to abort the study procedure and pursue a conventional stone removal procedure.

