In this study, the effectiveness of MONARCH™ in treating stones will be assessed from the post-operative Day 30 stone free rate, where stone free is defined as CT assessment showing  $\leq 4$  mm residual fragments. Subjects will undergo a mini-PCNL procedure with the MONARCH™ system. As an exploratory assessment of immediate post-operative stone clearance, the presence of any residual stones will be initially assessed by CT within 1 day of the procedure. Subsequently, subjects will undergo CT assessment 30-days post-procedure to measure the effectiveness of the procedure. However, to minimize radiation exposure, subjects without any residual fragments observed by CT at post-operative Day 1 will not undergo the additional CT at post-operative Day 30. Rather, these subjects will be presumed to be stone free at Day 30.

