Blood tests including the PT/INR coagulation test. These tests may be needed before the procedure to ensure that study patients have no problems related to blood clotting. Bleeding can sometimes occur after percutaneous renal procedures. The study patients will be asked to stop anticoagulants several days prior to the procedure.

The electronic version of this document is stored in Agile PLM and is considered the controlled copy.

Printed copies are for reference only and considered UNCONTROLLED.

CONFIDENTIAL AND PROPRIETARY OF AURIS HEALTH, INC.

	PROTOCOL	Doc #:	104-016667-00
	Monarch Uro - Post-Operative Outcomes Study (2023-URO-0001)	Rev:	C
		Page:	20 of 52

Preoperative Imaging: De-identified scans will be provided to the study Sponsor.

CT-KUB non contrast: Pre-op CT-KUB non contrast will be performed as part of the screening assessment, up to 120 days prior to the procedure.

Postoperative Follow-up Imaging: De-identified scans will be provided to the study Sponsor.

CT-KUB non-contrast: All patients will receive to determine remaining stone burden at Day 1. Patients with residual stones will have an additional CT-KUB non-contrast at Day 30. The secondary endpoint, stone free rate at Day 30, is the percentage of patients who are stone free assessed by CT, where stone free is defined as having  $\leq 4$  mm residual stones.

Fluoroscopy: Fluoroscopy will be used provide an additional viewing method during the procedure. De-identified images will be provided to the study Sponsor.

Endoscopy: Endoscopic ureteroscopy will be used to evaluate the presence of residual stone fragments in the kidney at the end of the procedure. Assessment will be recorded on CRFs.

Concomitant Medications. All medications beginning from 30-days prior to screening until subject exit will be recorded on a rolling medication log on the relevant case report forms.

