## **Secondary Endpoints**

Secondary endpoints in this study are:

- Stone free rate ( $\leq 4$  mm residual fragments, measured 30-days post-operative)
- Adverse events through 90-days post-operative, scored on the Clavien-Dindo scale
- Conversion to conventional treatment methods due to study device-related safety event

**Stone free rate:** This will be computed as the percentage of patients who are stone free assessed by CT at post-operative day 30. Stone free is defined as having  $\leq 4$  mm residual stones detected by CT. Patients who are found to not have any residual stone fragments at Day 1, will not undergo a second CT at post-operative Day 30, and will be presumed to be stone free at Day 30 for this calculation.

**Adverse events:** All adverse events will be captured up to post-operative Day 90, at which point the subject exits the study. See Section 7 below for description of how adverse events will be classified in this study. Adverse events will also be scored on the Clavien-Dindo scale. The Clavien-Dindo scale is system for grading the severity of postoperative complications (see Appendix III).

**Conversion to Conventional Treatment Methods Due to Study Device-Related Safety Event:** Number of procedures converted to conventional stone removal procedures (e.g., ureteroscopy or percutaneous nephrolithotomy) due to the occurrence of a study device-related safety event. A qualifying safety event, is a study device-related adverse event (see Section 7.1 below) that occurs during the study procedure, which prompts the physician to abort the study procedure, and pursue a conventional stone removal procedure. The conventional stone removal procedure need not occur within the same procedure. By contrast, conversion due to non-safety related device malfunction (e.g., unrecoverable fault observed from the ureteroscope robotic driver) will be captured separately, but will not count towards this endpoint. Similarly, conversion due to factors not related to the study device, but rather due to the patient's pre-existing condition (e.g., subject was not able to accommodate a ureteral access sheath during cystoscopy) will be documented as screen failures.

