- Subjects requiring retreatment for stone removal within the duration of the study, as reported within the Concomitant Procedure eCRF
- Responses to the Investigator Experience surveys regarding the procedure, retrograde instruments, antegrade instruments/controller, and user experience.

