## 8.10 Handling of Missing Data

All summaries will be performed only on subjects undergoing the scheduled procedure and only observed data will be summarized. There will be no imputation of data for early terminated subjects or for missing data within the database.

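### The Day-30 stone-free rate can count clearance achieved by conversion or retreatment, and its one-sided missing-data handling will tend to inflate it

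*SAP*

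**What the plan says.** Protocol 2.1 (Background) says that the effectiveness of MONARCH "in treating stones will be assessed from the post-operative Day 30 stone free rate". SAP 8.6 gives the rate as "computed as the percentage of patients who are stone free assessed by computed-tomography (CT) scan at post-operative Day 30", with a threshold of 4 mm cumulative residual burden. It adds: "The number and percentage of procedures resulting in a subject who is determined to be stone free at Day 30 will be" summarised with a 95% confidence interval. Neither sentence sets a condition on how the kidney became clear.

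The analysis set (SAP 6) is every subject with a recorded ureteroscope-introduction time, so a case converted after that moment stays in. Protocol section 6, on conversions prompted by a device-related safety event, says: "The conventional stone removal procedure need not occur within the same procedure". SAP 8.7 counts "Subjects requiring retreatment for stone removal within the duration of the study, as reported within the Concomitant Procedure eCRF" as a separate item.

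On imaging, Protocol 3.2 (Assessment schedule) says: "Patients with residual stones will have an additional CT-KUB non-contrast at Day 30". SAP 8.6 says of those whose first scan is completely clear that they "will not undergo a second CT at post-operative Day 30, and will be presumed to be stone free at Day 30 for this calculation". SAP 8.10 restricts summaries to observed data and adds: "There will be no imputation of data for early terminated subjects or for missing data within the database". SAP 8.12 plans no sensitivity analysis.

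**The concern.** There are two separate problems.

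**Attribution.** A robot malfunction followed by conversion fails the primary endpoint (Protocol section 6, SAP 8.5). The same procedure can then be a success in the stone-free rate if the conventional procedure cleared the kidney. A kidney retreated before the Day-30 CT is in the same position. Both events are foreseen and collected, but no section links either to stone-free status.

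**Missing data.** A subject clear at Day 1 cannot be missing at Day 30. Those who can be missing are the subjects with Day-1 fragments, plus any without a Day-1 CT. The guaranteed successes always stay in, while part of the group with a lower expected success rate can drop out.

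The study tests no hypothesis, so the estimate and its interval are the result. Protocol section 12 allows the data to be reused in publications and as a comparator or control arm in future studies, where an unclear definition would be carried along.

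**Working it through.** The plan states no expected rate, so there is no figure to reproduce. Sixty is an enrolment cap that was not statistically derived, and SAP 1.2 says enrolment stopped before it without giving the final number. Every rate below is an assumption.

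**1. Missing Day-30 CTs.** Let n be the number of procedures, c those clear at Day 1, r = n − c those with fragments, s the proportion of r that would be stone free at Day 30, and m the proportion of r with no Day-30 CT. If missingness is unrelated to outcome within r:

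- Complete-data rate = (c + rs)/n
- Rate as planned = (c + r(1−m)s) / (c + r(1−m))

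Take n = 50, c = 25, r = 25, s = 0.6, m = 0.2, so five CTs are missing, three of them from would-be successes.

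- Complete data: (25 + 15)/50 = 40/50 = 80.0%
- As planned: (25 + 12)/(25 + 20) = 37/45 = 82.2%, an excess of 2.2 points
- Missing as failure: 37/50 = 74.0%
- Missing as success: 42/50 = 84.0%

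Over c/n from 0.3 to 0.7, s from 0.4 to 0.6 and m from 0.1 to 0.3, the excess runs from 0.9 to 5.3 points. A second grid (c/n 0.4 to 0.7, s 0.25 to 0.75, same m) gives 0.5 to 6.6 points.

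**2. Is the direction fixed?** The complete-data rate is a weighted mean of the observed and missing groups, so

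excess = (fraction missing) × (success rate among observed − success rate among missing).

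In the example this is 0.10 × (82.2 − 60.0) = 2.2 points. Hold the complete-data rate at 40/50 = 80.0% and vary how many of the five missing would have succeeded:

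| Would-be successes among 5 missing | Rate as planned |
|---|---|
| 0 | 40/45 = 88.9% |
| 3 | 37/45 = 82.2% |
| 4 | 36/45 = 80.0% |
| 5 | 35/45 = 77.8% |

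The excess is upward until four of five would have succeeded, and downward only if all five would have. Residual subjects overall succeed at 60% in this example.

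**3. Conversion and retreatment.** If k of the successes were converted or retreated before the CT, counting them as not stone free lowers the rate by k/n. One procedure is worth 1/60 = 1.7 points, 1/50 = 2.0 points or 1/40 = 2.5 points. With k = 3 and complete data, the rate falls from 40/50 = 80.0% to 37/50 = 74.0%.

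**4. Both together.** The like-for-like gap is 82.2 − 74.0 = 8.2 points: 2.2 from missingness and 6.0 from attribution.

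**5. Scale.** The exact 95% interval for an observed 80% is 64.4 to 90.9% at 32/40 and 67.7 to 89.2% at 48/60. The shifts above are smaller than that uncertainty, but they are systematic and the interval does not account for them.

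**The case against.** The strongest reply is that the plan is silent on converted cases and does not expressly credit them. SAP 8.10 limits summaries to subjects who had the scheduled procedure, and Protocol section 6 records conversions due to patient factors as screen failures. If the rate is meant as the patient's status at Day 30 whatever treatment was given, counting converted or retreated kidneys is no bias. This stands in part: the documents never state which quantity is intended, so the fault is an unspecified rule. But the analysis set keeps cases converted after ureteroscope introduction, SAP 8.10 does not say whether a converted case had the scheduled procedure, and the protocol's stated use of the rate is to judge the device.

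A reader might infer that the missing-data rule can only remove failures, so that upward bias is certain. The documents do not support that. Residual subjects already at or below 4 mm on Day 1 meet the threshold yet drop out if the second CT is missed, and others may pass fragments by Day 30. Protocol 2.1 (Radiation) says one post-operative CT is standard practice, so subjects with trivial fragments may be the ones who skip the second.

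Much is visible elsewhere. Conversion fails the primary endpoint, device-safety conversions and retreatments are counted, and eCRF data are listed by subject. The Day-1 rate is unaffected by later retreatment or Day-30 missingness. Presuming Day-1-clear subjects stone free is disclosed and explained by radiation exposure. All of that is true, but a reader of the summary tables still cannot derive a device-attributable rate or bounds from separate counts.

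**Conclusion.** The point holds in a limited form. The Day-30 rate as written can include clearance achieved by other procedures, and its missing-data handling is asymmetric, with a probable but not certain upward effect. Missingness adds about 1 to 5 points under the assumed inputs. Relative to a device-attributable rate, attribution adds k/n, which is never negative.

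A reader might stack everything and claim a gap of about 14 points: 37/45 = 82.2% against (37 − 3)/50 = 68.0%. That overstates it. Six of those points (3/50) come from scoring three missing would-be successes as failures. The like-for-like gap is 8.2 points, and even that rests on invented counts.

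The endpoint is secondary in a descriptive study. No error rate is affected and the primary endpoint is untouched, so this should be fixed but does not undermine the study.

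**What to change.** Keep the protocol-defined CT-only rate. Replacing it now would be a late change of definition, since enrolment has stopped and three data summaries have been produced (SAP 8.9). Add to SAP 8.6 and 8.12, each with a 95% confidence interval:

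- **Device-attributable rate.** A procedure with any case conversion, or with stone retreatment of that kidney before the assessing CT, counts as not stone free. For the Day-1 rate, apply the conversion condition only.
- **Full-denominator analyses.** Keep all procedures in the Full Analysis Set and report missing-as-failure and missing-as-success bounds. As a sensitivity analysis, carry Day-1 status at the 4 mm threshold forward for residual subjects with no Day-30 CT.

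State in SAP 8.10 whether converted cases remain in the summaries. Carry-forward and the bounds are forms of imputation, which Protocol 8.5 and SAP 8.10 rule out, so label them as sensitivity analyses and make them an explicit exception.

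Cost: an SAP amendment (required by SAP 8.1) and a few extra tables, with no new visits or scans. This assumes the eCRFs record the date and side of any retreatment, which the documents do not state. The device-attributable figure will probably be lower than the headline rate.

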at the discretion of the physician (e.g., lower pole stones with > 10 mm stone burden). However, treatment with URS for larger stone sizes with acceptable outcomes has also been reported, suggesting a future where the threshold stone burden for recommending PCNL as a first-line therapy may be increased. The term “mini-PCNL” refers to the subset of PCNL procedures where the percutaneous tract size is  $\leq 20$  Fr, whereas standard PCNL has a tract size of up to 24-26 Fr. The MONARCH™ system includes a renal sheath with an 18 Fr inner diameter, and thus provides the instruments to perform a mini-PCNL procedure. There is no consensus as to the absolute range of stone burdens appropriate for mini-PCNL, and its use is determined by physician preference. This study will assess the performance and safety of MONARCH™ mini-PCNL in the treatment of patients with stone burdens appropriate for mini-PCNL, as appropriate by investigator assessment.

Indeed, there is considerable variation in reports of how effective these treatments truly are in rendering a patient stone-free. The assessment of stone-free may be influenced by the method used for detection post-operative stone assessment (e.g., CT, ultrasound, X-ray), the timing of this assessment relative to the procedure, and the definition of stone free (including “clinically insignificant” residual fragments up to a specified size threshold vs truly no residual stones). It has been reported that the presence of any residual stones post-procedure is associated with increased complications and increased occurrence of retreatment procedures, although these outcomes are influenced by the size of fragments, occurring more commonly in patients with fragments > 4 mm. Additionally, most studies in this field have focused on stone clearance outcomes after 30-90 days post-procedure, which does not readily distinguish between stone clearance that was achieved by a surgical tool and that from the spontaneous passage of stone fragments and dust.

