#### Secondary Endpoints

The following will be considered secondary endpoints:

- Stone free rate ( $\leq 4$  mm residual fragments, measured 30-days post-operative)
- Adverse events through 90-days post-operative, scored on the Clavien-Dindo scale (see Appendix III)
- Conversion to conventional treatment methods due to study device-related safety event

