##### *Pre-Operative:*

- Parameters of kidney stone number, size, density and location via CT
- PROs (baseline)

The electronic version of this document is stored in Agile PLM and is considered the controlled copy.

Printed copies are for reference only and considered UNCONTROLLED.

CONFIDENTIAL AND PROPRIETARY OF AURIS HEALTH, INC.

 AURIS	PROTOCOL	Doc #:	104-016667-00
	Monarch Uro - Post-Operative Outcomes Study (2023-URO-0001)	Rev:	C
		Page:	14 of 52

*Pre-Procedure:*

- Date and time patient admitted to hospital
- Cystoscopy phase timestamps and fluoroscopy use
- Patient positioning parameters

*Procedure:*

- Timestamps and additional parameters during procedure phases of device setup, ureteroscopy, percutaneous access, mini-PCNL setup, mini-PCNL procedure, and device teardown
- Intraoperative visualization
- Intraoperative fluidics management
- Intraoperative bleeding
- Conversion to conventional procedure (and reason for conversion)
- Presence of Randall's plaques
- Urologist experience survey

*Discharge and Follow-up:*

- Any placement of a ureteral stent or nephrostomy tube
- Date and time subject is discharged from hospital
- Any additional stone retreatment during follow-up
- Assessment of any residual stones via CT (post-operative Day 1 and Day 30 (as needed))
- PROs (post-operative Day 1, 30, and 90)

The following endpoints will be derived from the data collected:

- Percutaneous access success rate
- Percutaneous access time
- Procedure duration
- Hospital length of stay
- Radiation time and dosage
- Stone removal efficiency (stone burden/lasing time)
- Retreatment rate: post-operative Day 30 and Day 90
- Stone free rate: post-operative Day 1 and Day 30
  - Sub-analyses will include calculations using various thresholds for residual fragments (e.g., 0 mm,  $\leq 2$  mm, and  $\leq 4$ mm)

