#### 8.15 Exploratory Analyses

Counts and percentages (labeled as the “stone free rate”) will be provided for the number of procedures where post-operative cumulative stone burden is in the following categories: 0 mm,  $\leq 2$  mm, and  $\leq 4$ mm. Analyses of the following cohorts will be performed:

- All subjects receiving the study procedure
- Pre-operative stone burden (1-2 cm), representing “intermediate-sized stones”
- Pre-operative stone burden (1-3 cm), representing “classic mini-PCNL stones”
- Pre-operative stone burden (1-4 cm), representing “targeted patient pool”
- Pre-operative stone burden ( $> 2$  cm), representing “classic PCNL stones”
- Pre-operative stone burden ( $> 4$  cm), representing “very large-sized stone”

Summary statistics will be presented for the total volume of fluid input from the MONARCH™ fluidics pump and total volume of fluid collected in the waste management system.

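### SAP 8.6 computes the Day-30 stone-free rate on summed residual burden, while its own endpoint bullet and the protocol define it by fragment size

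*SAP*

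**What the plan says.** Protocol 3.1 and Section 6 list the secondary endpoint as a stone-free rate with at most 4 "mm residual fragments, measured 30-days post-operative". Section 6 then defines stone free as at most 4 "mm residual stones detected by CT". Protocol 3.2 describes the same quantity: the "stone free rate at Day 30, is the percentage of patients who are stone free assessed by CT", again with a 4 mm limit on residual stones. None of these passages adds fragments together.

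Protocol 2.1 reports that complications and retreatment after residual stones are "influenced by the size of fragments, occurring more commonly in patients with fragments > 4 mm". The derived endpoints in Protocol 3.1 carry the fragment wording into the 0, 2 and 4 mm cuts: "Sub-analyses will include calculations using various thresholds for residual fragments".

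SAP 8.6 repeats the fragment wording in its endpoint bullet. Its computing sentence then sets the criterion at no more than 4 "mm residual cumulative stone burden detected by CT". SAP 8.4 gives the meaning of that term: "cumulative stone burden, defined as the sum of the longest dimension of all stones". SAP 8.15 builds its exploratory stone-free rates on the same quantity, counting the "number of procedures where post-operative cumulative stone burden is in the following categories" of 0, 2 or less, and 4 or less mm. SAP 8.12 plans no sensitivity analysis.

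**The concern.** Protocol 2.1 says the effectiveness of the device will be judged from the Day-30 stone-free rate, so the definition matters even though the endpoint is secondary and descriptive. SAP 8.6 contains two definitions of it, and the one that drives the calculation is not the one in its own bullet or the one the protocol naturally conveys.

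A programmer following the computing sentence would put a summed-burden rate under the protocol's label. No other planned table gives the per-fragment rate, because the exploratory rates are also cumulative. The result would no longer match the protocol's reason for the 4 mm cut, which is stated in terms of fragment size. The SAP text neither marks nor explains the difference.

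**Working it through.** The plan gives no expected stone-free rate and no power calculation, so there is no figure to reproduce. The check compares the two rules.

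**Rules.** Let a procedure leave k residual fragments with longest dimensions d1, ..., dk in mm.

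- Per-fragment rule (protocol, natural reading): stone free if every di ≤ 4.
- Cumulative rule (SAP 8.6 with 8.4): stone free if d1 + ... + dk ≤ 4.

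**Direction.** All di are positive, so each di is no larger than the sum. If the sum is at most 4, every di is at most 4. The cumulative rule therefore implies the per-fragment rule, but not the reverse. Enumerating all ordered sets of 0 to 4 fragments from 0.5 to 8 mm in 0.5 mm steps (1 + 16 + 256 + 4,096 + 65,536 = 69,905 sets) found none that was stone free by the sum but not per fragment. It found no disagreement when k was 0 or 1.

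| Residual fragments (mm) | Per fragment | Sum (mm) | Cumulative |
|---|---|---|---|
| none | stone free | 0 | stone free |
| 4 | stone free | 4 | stone free |
| 2 + 2 | stone free | 4 | stone free |
| 3 + 2 | stone free | 5 | not |
| 3 + 3 | stone free | 6 | not |
| 2 + 2 + 2 | stone free | 6 | not |
| 5 | not | 5 | not |

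**Size.** The gap is an identity:

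per-fragment rate − cumulative rate = share of procedures with two or more fragments, each ≤ 4 mm, summing to more than 4 mm.

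The documents do not give this share. SAP 8.4 says many subjects present with more than one stone, and SAP 8.7 tabulates the number of post-operative stones, so multiple residuals are foreseeable. Neither statement yields a frequency.

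**Illustration only.** Assume 60 procedures (the planned maximum; the SAP says enrolment stopped short of it) and a per-fragment rate of 54/60. Intervals are exact 95%, chosen here because the SAP names no method for this endpoint.

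| Assumed share reclassified | SAP rate | 95% CI |
|---|---|---|
| 0% | 54/60 = 90.0% | 79.5 to 96.2 |
| 5% | (54 − 3)/60 = 85.0% | 73.4 to 92.9 |
| 10% | (54 − 6)/60 = 80.0% | 67.7 to 89.2 |
| 20% | (54 − 12)/60 = 70.0% | 56.8 to 81.2 |

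With 40 procedures and 10% reclassified, 36/40 = 90.0% (76.3 to 97.2) becomes 32/40 = 80.0% (64.4 to 90.9).

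**SAP 8.15 categories.** At 0 mm the rules are identical, because zero total burden means no fragments. At 2 mm they can differ: 2 + 1 mm passes per fragment, but the sum is 3 mm. At 4 mm they differ as tabulated above.

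**Day 1 and the Day-30 presumption.** The Day-1 rate takes the same definition, since SAP 8.6 says it will be analysed similarly. The rule that a clear Day-1 CT counts as stone free at Day 30 is unaffected, because no fragments satisfies both definitions.

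**The case against.** The best defence is that the protocol is not explicit. It never says largest, single or each fragment, and a limit of 4 mm on residual stones could be read as a total. Protocol 3.2 says the Day-1 CT is to determine remaining stone burden just before it defines the endpoint. Protocol Section 8 leaves detailed analyses to the SAP, so the SAP may be settling an ambiguity. This stands in part: the per-fragment rule is the natural reading, supported by Protocol 2.1 and the threshold list in 3.1, but it is not literal protocol text. It does not explain why one SAP section carries both definitions.

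It is also fair that SAP 8.4 defines cumulative burden for pre-operative and procedure-day data. Applying that definition at follow-up is an inference, though SAP 8.7 uses the same term for the 30-day visit.

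Four stronger readings are tempting and are not supported:

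- A reader might infer that the rule flatters the device. It cannot; it can only lower the rate.
- A reader might infer a data-driven choice, because the SAP describes stopped enrolment and three data summaries in the past tense. Protocol Section 8 requires SAP approval only before final database lock, and SAP 8.9 does not say the summaries held stone-free results.
- A reader might assume fragment sizes and quote a definite loss in percentage points. The answer would follow from the assumption: two fragments of 2 mm or less, for instance, never exceed 4 mm in total.
- A reader might take all three SAP 8.15 thresholds to be affected. The 0 mm category is not.

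Finally, the study tests no hypothesis, the primary endpoint is untouched, and SAP 8.1 promises per-subject listings. That limits the severity. It does not supply a planned table with the per-fragment rate.

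**Conclusion.** SAP 8.6 is internally inconsistent and departs from the protocol's natural per-fragment definition of the Day-30 stone-free rate. The effect runs one way: the planned rate equals the per-fragment rate or is lower. It equals it exactly if no procedure leaves several small fragments summing to more than 4 mm. Otherwise it is lower by the share of procedures that do, which the documents do not reveal; the illustrated drop from 90.0% to 80.0% rests on an assumed 10% share and an assumed starting rate.

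The fault is an unmarked difference in what is measured under the protocol's label, not bias in the device's favour. It should be fixed, but as a descriptive secondary endpoint it does not threaten the study's primary result. The conclusion assumes that cumulative burden at follow-up means the sum defined in SAP 8.4.

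**What to change.** In SAP 8.6, for both Day 1 and Day 30, state that a procedure is stone free when every residual fragment on CT has a longest dimension of 4 mm or less. Describe this as consistent with the protocol's fragment-size wording and rationale rather than as its literal text. Apply the same per-fragment rule to the 2 mm and 4 mm rows in SAP 8.15; the 0 mm row needs no change. Report the cumulative-burden rate as a separately labelled supplementary row.

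If the sponsor prefers the cumulative rule, the SAP should record it as a change from the protocol, give the reason, align the endpoint bullet, and report both rates.

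The cost is SAP wording and an extra table row. This assumes that the post-operative dimension of each stone is recorded. The cumulative sum as defined in SAP 8.4 needs those dimensions, but the case report forms are not part of the documents, so this should be confirmed.
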